## 8.2. Safety Data Presentation and Analysis

All clinical safety and tolerability data will be listed for each subject.

Safety data will be presented for all subjects in the safety analysis set and summarised by dose level / treatment group.

Safety data will be summarized descriptively in tabular form. Summaries of key safety data assessed over time may also be presented in graphical form, as appropriate. Where summaries include changes from baseline, the relevant baseline value will be determined as described in Section 5.5 above.

All treatment-emergent adverse events reported in this study will be presented using MedDRA terms, as coded per the Data Management Plan. AEs and SAEs with onset following administration of the investigational product will be summarised by dose level / treatment, grouped according to system organ class and preferred term, and tabulated with descriptive statistics, where appropriate, for number of subjects and number of AEs per category, for all AEs and for AEs deemed drug-related. AEs will also be summarised by severity and by relationship to investigational product. Where a subject has more than one AE for the same MedDRA category, the subject will be counted only once, for the AE of highest severity or least favourable relationship.

Prior and concomitant medication will be coded using the WHO Drug Dictionary (WHODrug), as coded per the Data Management Plan. The number and percentage of subjects taking prior medication, and concomitant medication will be summarised using frequency tables according to WHO Drug ATC Level 1 Code Description and the WHO Drug Dictionary Preferred Name. If a subject has more than one prior or concomitant medication coded to the same category, the subject will be counted only once.

Clinical laboratory parameters will be tabulated and summarised by dose level / treatment group and study time point. A summary of changes from baseline will also be presented for clinical laboratory parameters. Medical assessments of blood and urine parameters will be summarised by treatment group and study time point. Individual subject profiles will be presented for any laboratory parameters with at least one post-dose value outside the laboratory's reference ranges and deemed clinically significant.

Vital signs (systolic/diastolic blood pressure, heart rate, body temperature and respiratory rate) will be tabulated and summarised by dose level / treatment and study time point, separately for supine and standing. A summary of changes from baseline will also be presented.

Changes from screening or previous visit in physical examination findings will be listed for each subject. It is noted that any untoward findings identified on physical and neurological examinations after the start of administration of the study medication will be captured as an adverse event if those findings meet the definition of an adverse event as defined in the protocol.

Local skin reactions (LSRs) (including burning/stinging, erythema, erosions, and edema) will be summarized by frequency of each individual LSR for each treatment group. Change from Baseline in LSRs will be categorized into 'worsened' and 'same or improved' and will be tabulated.

## **9. EFFICACY DATA**

### **9.1. Efficacy Data Presentation**

#### **9.1.1. VIIS**

VIIS scores will be listed, for each body area, per subject, per visit. Body areas will be identified as target or non-target and this information will be provided in the individual listing as well. Descriptive statistics (including frequencies and percentages) for observed, change from Baseline values in VIIS scaling at each visit, success rate, as well as a shift table will be presented by treatment group for each CI subtype and overall. VIIS scaling is defined as the average of the severity scores for the VIIS body areas, where the numerator is the sum of the severity scores and denominator is the number of body areas assessed at that visit. Success is defined as a  $\geq 50\%$  reduction at Visit 6 relative to Baseline in the sum of VIIS scores for target body sites that had a Baseline score  $\geq 3$ . That is, a participant is flagged as treatment success if, at Visit 6 (or EOS), the sum of the VIIS scores for the same target body sites identified at Baseline is  $\geq 50\%$  lower than the sum of VIIS scores for these target body sites at Baseline. Results from Cochran-Mantel-Haenszel test at Visit 6 (EOS) will be presented together with corresponding 95% confidence intervals. Time from baseline to treatment success will be estimated using KM analysis and individual results will be listed and summarized using descriptive statistics.

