4.1.2.1 Treatment Area

The area of the entire body with active CI where the study medication will be applied (the entire body except for the hands, face, neck, scalp and genitalia are possible treatment areas.)

4.1.2.2 *The Visual Index for Ichthyosis Severity (VIIS) Assessment Areas*

The primary efficacy assessment will be performed using the Visual Index for Ichthyosis Severity (VIIS). Four VIIS Assessment Areas will be defined as described below and will be further described using color illustrations in the Investigator Study Binder:

- (a) the upper back from the posterior axillary fold to the other encompassing the T1-T10,
- (b) the upper arm (excluding elbow), left or right,
- (c) the shin/lower leg (the portion below the proximal aspect of the knee cap), left or right
- (d) dorsal foot (left or right).

The Investigator will include subjects when any of the 4 VIIS Assessment Areas have some CI disease. At least 2 of the 4 VIIS Assessment Areas MUST have a scaling score of 3 or more. Since for (b), (c), and (d) each include two body parts, one of each left or right must be designated as the Target (upper arm, lower leg, or dorsal foot) and followed throughout the study for VIIS assessment. The arm, leg, or foot with more severe and higher score will be designated as the Target unless they have the same severity scores, in which case the left or right choice will be at the discretion of Investigator assuming no other issues exists, dictating the choice of left/right. The severity scores will be averaged by the electronic data capture system but the score of two body parts that have a score of 3 or higher will be used to enroll subjects and used in subsequent assessments. A five-point (0-4) scale will be used with increasing clinical severity (scaling) and will be defined in the training manual.

The primary efficacy endpoint will be the proportion of subjects with VIIS "treatment success" (VIIS-50), which is defined as a 50% or greater decrease in VIIS scaling score relative to Baseline at Visit 6, End of Study (EOS) calculated using **only** the VIIS body areas described above that have a Baseline score ≥ 3 .

VIIS severity will be calculated as above via one of two methods below

- On-site visual inspection of the VIIS areas

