#### 4.6. Study Endpoints

##### 4.6.1 Efficacy Endpoints

###### 4.6.1.1 Primary Efficacy:

- Proportion of subjects with VIIS "treatment success" (VIIS-50), which is defined as a 50% or greater decrease at Visit 6 (EOS) relative to Baseline in the sum of the scores for VIIS target sites that have a Baseline score of  $\geq 3$ .

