## 5.6. Handling of Missing Data

### 5.6.1. Efficacy Missing Data Rules:

Data summaries and analyses will use observed data only without imputation of missing values. Supplementary analysis will be performed to investigate the impact of data imputation on the primary endpoint as follows:

- 1) by assuming that subjects with missing data are treatment successes (“best case”) and
- 2) by assuming that subjects in the vehicle group with missing data are “treatment success” and that subjects in the TMB-001 groups with missing data are treatment failures (“worst case”) and
- 3) by assuming that subjects with missing data maintain their last observed rating from which treatment success or failure will be derived at Visit 6 (“LOCF”) and
- 4) by assuming that subjects with missing data are treatment failures (“non-responder”)

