### 9.2.2. Secondary Efficacy Endpoints

- The proportion of subjects achieving IGA treatment success will be the key secondary endpoint. The IGA score will be dichotomized to “treatment success” or

“treatment failure” where “treatment success” is defined as at least a 2-grade decrease in severity score relative to Baseline. Active treatment will be compared with vehicle at Visit 6 (EOS) using the CMH test stratified by CI subtype and 95% confidence intervals will be calculated for the difference in proportions for the treatment groups.

Other Secondary Endpoints:

- The time to achieve VIIS-50 ( $\geq 50\%$  reduction in VIIS scaling score for body sites that had a Baseline score  $\geq 3$ ) that is maintained at the next observation. If VIIS-50 is first achieved at Visit 6 (EOS), then the endpoint is considered to have been met. A time to event analysis will be performed using the Kaplan-Meier (K-M) method and log rank test to compare active treatment with vehicle. The results from K-M analysis will be tabulated as well as graphically presented.
- Changes in VIIS scaling score relative to Baseline at Visit 4 and Visit 5:  
The treatment groups will be compared with respect to the change from Baseline using mixed model of repeated measures (MMRM) including terms for treatment, visit, treatment by visit interaction, and the Baseline VIIS scaling score serving as the covariate. VIIS scaling score is defined as the average score of grades for all body areas assessed at that visit. From the model, the active to vehicle treatment differences will be estimated. Additionally, two-sided confidence intervals will be provided.
- Proportion of subjects with IGA “treatment success” at Visit 4, Visit 5, and Visit 6 (EOS):  
Descriptive statistics (including frequencies and percentages) for IGA success rate will be presented by treatment group for each CI subtype and overall. Success is defined as a  $\geq 2$ -point reduction in IGA score from Baseline.
- Proportion of subjects with IGA score representing “cleared” or “almost cleared” at Visit 6 (EOS):  
Descriptive statistics (including frequencies and percentages) for IGA scores representing “cleared” or “almost cleared” will be presented by treatment group for each CI subtype and overall. “Cleared” or “Almost cleared” is defined as an IGA score of 0 or 1.
- Changes in percent BSA relative to Baseline with CI in the Treatment/Assessment Areas at Visit 3, Visit 4, Visit 5, and Visit 6 (EOS):  

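### The VIIS scaling average is taken over whichever areas were scored at that visit, so a skipped area can move change from Baseline with no change in disease; VIIS-50 needs one sentence on a partly scored Visit 6

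*SAP*

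**What the plan says.** Two different VIIS quantities are in use.

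**The average.** SAP 9.1.1 defines VIIS scaling as a sum of severity scores divided by a count, where the "denominator is the number of body areas assessed at that visit". SAP 9.2.2 repeats this for the secondary endpoint: "VIIS scaling score is defined as the average score of grades for all body areas assessed at that visit". Neither section requires the areas at a visit to match those at Baseline. The score feeds the change-from-Baseline and shift tables (9.1.1), the secondary MMRM for Visits 4 and 5 (9.2.2) and the pooled-active MMRM (9.2.3).

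**The primary sum.** SAP 4.6.1.1 defines VIIS-50 as "a 50% or greater decrease at Visit 6 (EOS) relative to Baseline in the sum of the scores" over target sites that scored 3 or more at Baseline. SAP 9.1.1 says how the Visit 6 side is formed: it is "the sum of the VIIS scores for the same target body sites identified at Baseline", set against the Baseline sum for those sites. The entry rule in Protocol 4.1.2.2 is "At least 2 of the 4 VIIS Assessment Areas MUST have a scaling score of 3 or more", so two is the smallest possible number of qualifying sites.

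**Missing data.** SAP 5.6.1 states: "Data summaries and analyses will use observed data only without imputation of missing values". Its four supplementary analyses (best case, worst case, LOCF, non-responder) are written for subjects with missing data. None addresses one unscored area within a visit that was otherwise scored.

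**Conduct.** Protocol 8.2 intends the areas defined at Baseline to be assessed at each visit. Protocol 8.1.2 to 8.1.4 allow Visits 2 to 6 to be held remotely. Protocol 8.2.1 bases remote scoring on photographs together with live video.

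**The concern.** A change score should compare like with like. When the denominator follows the areas scored on the day, losing a severe area lowers the average and losing a mild one raises it. The MMRM, the change tables and the shift tables would all read that movement as response or worsening. The observed-data rule gives no protection, because the subject has a score at that visit.

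The primary endpoint raises a related but separate question. Nothing states what happens to VIIS-50 if a target site is unscored at Visit 6. If the remaining scores were added up and compared with the full Baseline sum, the gap itself would count as improvement. A success produced that way would remain a success in all four supplementary analyses. The subject could also stay in the per-protocol set, because SAP 6.2 asks only for a VIIS measurement at Visit 6. The study is meant to inform Phase 3 dose selection and sample size (SAP 4.5) with 15 subjects per arm, so a few misclassified subjects would be noticeable.

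**Working it through.** The plan states no figure for this point, so there is none to reproduce. The check takes subjects whose disease does not change and asks what an unscored area does to each quantity.

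**Inputs.** Scores run from 0 to 4, there are four assessment areas, and at least two must score 3 or more (Protocol 4.1.2.2). A target site therefore scores 3 or 4 at Baseline. The VIIS-50 threshold is a 50% fall (SAP 4.6.1.1). There are 15 subjects per arm (SAP 4.5).

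**1. The average.** Let n areas be scored at Baseline, and let the one with score x be unscored later. With no disease change,

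shift = (mean of the other n - 1 scores - x) / n.

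- 4, 3, 3, 2: Baseline 12/4 = 3.00. With the 4 unscored, 8/3 = 2.67, a shift of -0.33.
- 4, 3, 1, 1: Baseline 9/4 = 2.25. With the 4 unscored, 5/3 = 1.67 (-0.58). With a 1 unscored, 8/3 = 2.67 (+0.42).
- 3, 3, 3, 3: no shift, because the lost score equals the mean of the others.
- Extremes for four areas in an eligible subject: losing the 4 from 4, 3, 0, 0 gives (1 - 4)/4 = -0.75. Losing the 0 from 4, 4, 4, 0 gives (4 - 0)/4 = +1.00.

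Eligible four-area patterns number 6×4×9 + 4×8×3 + 16 = 328, which gives 328×4 = 1312 ways to lose one area. The average moves in 1256 of these (95.7%). These are counts of possible patterns, not probabilities in the trial.

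**2. The primary sum, if only the scores present at Visit 6 were added.** The apparent fall is (sum of unscored Baseline scores) / (sum of all target Baseline scores).

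| Target sites | Unscored | False successes | Largest apparent fall |
|---|---|---|---|
| 2 | 1 | 6 of 8 | 4/7 = 57.1% |
| 3 | 1 | 0 of 24 | 4/10 = 40.0% |
| 4 | 1 | 0 of 64 | 4/13 = 30.8% |
| 3 | 2 | 24 of 24 | 8/11 = 72.7% |
| 4 | 2 | 66 of 96 | 8/14 = 57.1% |

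With two targets, 3+3 becomes 3 (50.0%), 4+4 becomes 4 (50.0%), and 4+3 with the 4 unscored becomes 3 (57.1%). With 4+3 and the 3 unscored the fall is 3/7 = 42.9%, which is not a success. With three targets, one gap needs help from real improvement: 3, 3, 3 with one site unscored and a 1-point gain in the other two shows 1 - 4/9 = 55.6%. The fall would be 1 - 6/9 = 33.3% if all three had gained 1 point.

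One such success changes an arm's rate by 1/15 = 6.7 percentage points.

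**3. With matched areas.** For 4, 3, 3, 2 with the 4 unscored, both visits average (3+3+2)/3 = 2.67 and the change is 0. The same holds for any unchanged subject.

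**The case against.** The strongest objection concerns the primary endpoint, and most of it stands. A reader might infer that the visit-specific denominator corrupts VIIS-50, or that the SAP prescribes a calculation that creates false successes. The text does not support either. The denominator belongs only to the average. VIIS-50 is a sum, and SAP 9.1.1 fixes its sites as those identified at Baseline. A sum over fewer sites is not that quantity, and leaving a site out of Visit 6 alone amounts to scoring it 0, which sits badly with a rule against imputation. The natural reading is that the outcome is missing. What remains is that neither 9.1.1 nor 5.6.1 says so.

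The likelihood can also be overstated. A reader might take remote visits as evidence that gaps will be common. Remote scoring uses live video as well as photographs, target areas are to be followed throughout, and Protocol 8.1.4 asks for every effort to hold Visit 6 on site. No rate of unscored areas is given. Whether the electronic data capture system accepts a blank area is not stated.

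Larger shifts in the average can be constructed. For example, 3, 3, 0, 0 moves from 1.50 to 3.00 if both zeros go unscored. That needs two gaps, both in disease-free areas, which may not belong to the subject's set at all, since Protocol 5.1 (criterion 6) refers to areas with some disease.

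A count that differs between subjects is also legitimate, because subjects may have different numbers of affected areas (Protocol 8.2.4, second example). The weakness is a count that can differ within a subject between visits. Finally, the listings by body area in SAP 9.1.1 would make a gap visible, but they would not correct the score.

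**Conclusion.** For the average the point holds on the text: the stated rule gives a wrong change from Baseline whenever a Baseline area is unscored, unless its score equals the mean of the others. With one area of four missing and no change in disease, the error lies between -0.75 and +1.00. This affects secondary and exploratory analyses and descriptive tables, not the primary endpoint.

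For VIIS-50 the point is a request for clarification. The site set is already fixed; only the consequence of a partly scored Visit 6 is unstated. A false success in an unchanged subject requires the partial-sum reading and, with a single gap, exactly two target sites.

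These sizes are per subject. The effect on treatment comparisons cannot be estimated, because the documents give no frequency of unscored areas and no indication of whether gaps would differ between arms.

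**What to change.** In SAP 9.1.1 and 9.2.2, fix each subject's set of VIIS areas at Baseline. Compute change at each visit only over areas scored at both Baseline and that visit, and use the same matched set in the change and shift tables. State that the MMRM covariate remains the full-set Baseline average; otherwise a subject could have several Baseline values in one model.

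In SAP 5.6.1, with a cross-reference from 9.1.1, add one confirming sentence: if any target site that scored 3 or more at Baseline is unscored at Visit 6, VIIS-50 is missing for that subject and the 5.6.1 analyses, including non-responder, apply.

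The cost is a few sentences and possibly a few more missing primary outcomes. At a partly scored visit the matched change will not equal the visit average minus the covariate, so a table footnote should say so. Matching also takes the unscored area to have changed, on average, as the scored ones did. That is an assumption, but a milder one than letting the mix of areas change.

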#### **9.1.2. IGA**

IGA scores will be listed per subject, per visit. Descriptive statistics (including frequencies and percentages) for observed, change from Baseline values in IGA at each

visit, success rate, as well as a shift table will be presented by treatment group for each CI subtype and overall. Success is defined as a at least 2-grade decrease in severity score relative to baseline. Time from baseline to treatment success will be estimated using KM analysis and individual results will be listed and summarized using descriptive statistics.

### 9.1.3. I-NRS

I-NRS scores at each visit and change from baseline at each visit will be listed per subject for Visit 2 (Baseline), Visit 5, and at Visit 6 (EOS). Descriptive statistics (including frequencies and percentages) for observed and change from Baseline values in I-NRS at each visit, success rate as well as a shift table will be presented by treatment group for each CI subtype and overall. Success is defined as  $\geq 4$ -point reduction from Baseline. Results from Cochran-Mantel-Haenszel test at Visit 6 (EOS) will be presented together with corresponding 95% confidence intervals.

### 9.1.4. DLQI

DLQI scores will be listed per subject for Visit 2 (Baseline), Visit 5, and at Visit 6 (EOS). Descriptive statistics (including mean, median, SD, min, and max) for observed and change from Baseline values in DLQI at each visit will be presented by treatment group for each CI subtype and overall. Subgroup analysis using descriptive statistics for observed and change from baseline values in DLQI at each visit will be performed on subjects with DLQI less than 10 and greater or equal to 10 at baseline. The same subgroup analysis will be performed for CDLQI values, where the subgroups will be: a score less than 13 on CDLQI at baseline vs score of 13 or more on CDLQI at baseline. Proportion of subjects with DLQI improvement of 4 or greater points from baseline will be described using frequency tables.

### 9.1.5. Percent BSA affected

Descriptive statistics (including mean, median, SD, min, and max) for observed and change from Baseline values in percent BSA affected in the Treatment/Assessment Areas at each visit will be presented by treatment group for each CI subtype and overall.

## 9.2. Efficacy Analysis

Efficacy analyses will be performed on both the ITT and PP populations with the ITT population considered primary.

### 9.2.1. Primary Efficacy Endpoint

The proportion of subjects achieving VIIS-50 ( $\geq 50\%$  reduction from Baseline for VIIS scaling score for the sum of the scores for ‘VIIS target body areas’ who had a Baseline score  $\geq 3$ ) at Visit 6 (EOS) relative to Baseline will be the primary efficacy endpoint. Treatment groups will be compared at Visit 6 (EOS) using the Cochran-Mantel-Haenszel (CMH) Test stratified by CI subtype and corresponding 95% confidence intervals will be calculated for the difference in proportions for the treatment groups. The proportion of subjects achieving VIIS-50 will be the response variable in the CMH test.

### 9.2.2. Secondary Efficacy Endpoints

- The proportion of subjects achieving IGA treatment success will be the key secondary endpoint. The IGA score will be dichotomized to “treatment success” or

“treatment failure” where “treatment success” is defined as at least a 2-grade decrease in severity score relative to Baseline. Active treatment will be compared with vehicle at Visit 6 (EOS) using the CMH test stratified by CI subtype and 95% confidence intervals will be calculated for the difference in proportions for the treatment groups.

Other Secondary Endpoints:

- The time to achieve VIIS-50 ( $\geq 50\%$  reduction in VIIS scaling score for body sites that had a Baseline score  $\geq 3$ ) that is maintained at the next observation. If VIIS-50 is first achieved at Visit 6 (EOS), then the endpoint is considered to have been met. A time to event analysis will be performed using the Kaplan-Meier (K-M) method and log rank test to compare active treatment with vehicle. The results from K-M analysis will be tabulated as well as graphically presented.
- Changes in VIIS scaling score relative to Baseline at Visit 4 and Visit 5:  
The treatment groups will be compared with respect to the change from Baseline using mixed model of repeated measures (MMRM) including terms for treatment, visit, treatment by visit interaction, and the Baseline VIIS scaling score serving as the covariate. VIIS scaling score is defined as the average score of grades for all body areas assessed at that visit. From the model, the active to vehicle treatment differences will be estimated. Additionally, two-sided confidence intervals will be provided.
- Proportion of subjects with IGA “treatment success” at Visit 4, Visit 5, and Visit 6 (EOS):  
Descriptive statistics (including frequencies and percentages) for IGA success rate will be presented by treatment group for each CI subtype and overall. Success is defined as a  $\geq 2$ -point reduction in IGA score from Baseline.
- Proportion of subjects with IGA score representing “cleared” or “almost cleared” at Visit 6 (EOS):  
Descriptive statistics (including frequencies and percentages) for IGA scores representing “cleared” or “almost cleared” will be presented by treatment group for each CI subtype and overall. “Cleared” or “Almost cleared” is defined as an IGA score of 0 or 1.
- Changes in percent BSA relative to Baseline with CI in the Treatment/Assessment Areas at Visit 3, Visit 4, Visit 5, and Visit 6 (EOS):  
Descriptive statistics (including mean, median, SD, min, and max) for observed and change from Baseline values in percent BSA at each visit will be presented by treatment group for each CI subtype and overall.
- Change from Baseline in Itch-Numeric Rating Scale (I-NRS) score at Visit 6 (EOS):  
The treatment groups will be compared with respect to the change from Baseline using mixed model of repeated measures (MMRM) including terms for treatment, visit, treatment by visit interaction, and the Baseline I-NRS value serving as the covariate. From the model, the active to vehicle treatment differences will be estimated. Additionally, two-sided confidence intervals will be provided.

- Change in DLQI from Baseline to Visit 6 (EOS):  
Descriptive statistics (including mean, median, SD, min, and max) for observed and change from Baseline values in DLQI and CDLQI at each visit will be presented by treatment group for each CI subtype and overall.

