6.3 Measures to Minimize Bias: Randomization and Blinding

Subjects who meet all inclusion criteria and no exclusion criteria will be randomized to a treatment group in a 1:1:1 ratio, stratified by CI subtype.

All subjects will be centrally assigned to randomized study treatment using an Interactive Web Response System (IWRS). Before the study is initiated, the log in information and directions for the IWRS will be provided to each study center.

Study medication use will be accounted and dispensed at the study visits as summarized in the Schedule of Activities ([Section 1.2](#)).

In this double-blind study, all personnel involved, ie, physicians, site staff, and participants will remain blinded at all times, except in an emergency, where knowledge of the randomization code is required to provide appropriate treatment. In case of an emergency, the Investigator has the sole responsibility for determining if unblinding of a subject's treatment assignment is warranted. Subject safety must always be the first consideration in making such a determination. If the Investigator decides that unblinding is warranted, every effort should be made to contact the Sponsor and Medical Monitor prior to unblinding a subject's treatment assignment unless this could delay emergency treatment of the subject. If a subject's treatment assignment is unblinded, the Sponsor must be notified within 24 hours after breaking the blind. The date and reason that the blind was broken must be recorded in the source documentation and electronic Case Report Form (eCRF), as applicable.

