### 5.2. Randomization and Subject Identification Code

Subjects who meet all inclusion criteria and no exclusion criteria will be randomized to a treatment group in a 1:1:1 ratio, stratified by CI subtype.

All subjects will be centrally assigned to randomized study treatment using an Interactive Web Response System (IWRS). Before the study is initiated, the log in information and directions for the IWRS will be provided to each study center.

Study medication use will be accounted and dispensed at the study visits as summarized in the Schedule of Activities (Section 1.2 of the protocol).

Subjects will be assigned a randomization number formatted, Rsnn where s is an indicator for the CI subtype (1 = ARCI-LI, 2 = RXLI) and nn is the random permutation of 01 - 45.

The listings for inclusion in an appendix to the clinical study report will be prepared after the study has been unblinded.

In the listings, subjects will be identified by subject number (assigned at randomization), with treatment as a secondary grouping identifier. Screening number will be shown only on the listing of informed consent data and screen failure data.

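### Low-cost improvement: CI subtype, the only randomisation stratum, is left out of the four VIIS and I-NRS MMRMs and the log-rank test of time to VIIS-50

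*SAP*

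**What the plan says.** Protocol 6.3 states that eligible subjects "will be randomized to a treatment group in a 1:1:1 ratio, stratified by CI subtype", and SAP 5.2 repeats it. No other stratification factor is named. SAP 5.2 gives no block size; it describes a randomization number with one digit for subtype, in which "nn is the random permutation of 01 - 45".

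The two leading analyses respect the stratum. The primary comparison in SAP 9.2.1 is a "Cochran-Mantel-Haenszel (CMH) Test stratified by CI subtype". The IGA key secondary in SAP 9.2.2 is compared "using the CMH test stratified by CI subtype and 95% confidence intervals will be calculated".

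The remaining inferential models do not:

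- **MMRMs.** The VIIS model in SAP 9.2.2 is described as "including terms for treatment, visit, treatment by visit interaction, and the Baseline VIIS scaling score serving as the covariate" and the I-NRS model as "including terms for treatment, visit, treatment by visit interaction, and the Baseline I-NRS value serving as the covariate". SAP 9.2.3 gives the two pooled-active models the same terms.
- **Log-rank tests.** For time to VIIS-50, SAP 9.2.2 says: "A time to event analysis will be performed using the Kaplan-Meier (K-M) method and log rank test to compare active treatment with vehicle". SAP 9.2.3 has three more log-rank tests, for time to a 2-point IGA decrease and times to scores of 0 and 1. Their stated purpose is only to describe those times. None of the four names a stratum.

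Protocol 9.4.1.2 lists the same MMRM terms and the same unstratified log-rank test. Neither document has a general rule that adds subtype to these models or a reason for leaving it out. Elsewhere among these endpoints, subtype serves as a grouping for descriptive tables.

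**The concern.** Stratified allocation balances the arms on subtype, so the between-subtype part of the outcome cancels from the treatment contrast. A model without subtype still counts that variation as residual noise. If subtype matters beyond the Baseline score, the reported standard error is larger than the true sampling error, the interval is too wide and the test is conservative.

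The stake is modest. SAP 4.5 describes 45 subjects chosen without a power calculation, to supply initial VIIS data for sizing later studies and to help choose a Phase 3 dose. The intervals for each concentration against vehicle bear on that choice, and with 15 per arm there is little precision to spare.

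**Working it through.** **Inputs from the documents.** Three arms of 15; two subtypes; one stratification factor; VIIS at four post-Baseline visits; I-NRS at two (Visits 5 and 6, Protocol 8.2.3). The only planning figure is 3 × 15 = 45. With no effect size, SD or power stated, there is no calculation to reproduce.

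**Assumptions.** Residual SD 1; true effect of one concentration 1 SD; between-visit correlation 0.6; Baseline slope 0.5; complete data; two-sided 5% tests; arms exactly balanced within subtype. The subtype gap d (in residual SDs, beyond Baseline) and the split per arm (8/7 or 12/3) were varied.

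**Step 1: closed form.** With subtype share p, omitting subtype raises the residual variance from 1 to about 1 + p(1−p)d², so the reported SE is inflated by √(1 + p(1−p)d²).

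- 8/7: p(1−p) = 56/225 = 0.249. At d = 0.5, √1.062 = 1.031; at d = 1, √1.249 = 1.118.
- 12/3: p(1−p) = 0.16. At d = 0.5, √1.04 = 1.020; at d = 1, √1.16 = 1.077.

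A finite-sample version divides the subtype sum of squares, 45p(1−p)d², by the 41 residual degrees of freedom of a single-visit model with three arms and a Baseline slope. For 8/7 at d = 1 this is 11.2/41 = 0.273, and √1.273 = 1.128, close to the simulated 1.126.

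**Step 2: MMRM simulation** (20,000 trials per cell, unstructured covariance, Monte Carlo error about 0.3 point).

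| Contrast | Split | d | Power, omitted | Power, added | SE excess |
|---|---|---|---|---|---|
| VIIS, Visit 5 | 8/7 | 0 | 75.8% | 75.7% | – |
| | 8/7 | 0.25 | 75.2% | 75.7% | 0.8% |
| | 8/7 | 0.5 | 73.6% | 75.6% | 3.3% |
| | 8/7 | 0.75 | 70.4% | 75.3% | 7.3% |
| | 8/7 | 1 | 66.9% | 75.6% | 12.6% |
| | 12/3 | 0.5 | 73.7% | 75.1% | 2.1% |
| | 12/3 | 1 | 70.1% | 75.3% | 8.3% |
| I-NRS, Visit 6 | 8/7 | 0 | 75.3% | 75.3% | – |
| | 8/7 | 0.5 | 73.1% | 75.4% | – |
| | 8/7 | 1 | 66.9% | 75.5% | – |

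At 1 SD (VIIS, 8/7) the true SD of the estimate is 0.371 without subtype and 0.369 with it, but the reported SE is 0.412 against 0.366. Type I error is 2.7% against 4.8%.

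Hand check with a critical value of 2.02: omitted, 2.02 × 0.412 = 0.832 and (1 − 0.832)/0.371 = 0.45, giving about 67%. Added, 2.02 × 0.366 = 0.739 and (1 − 0.739)/0.369 = 0.71, giving about 76%.

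A separate single-visit simulation, set up by the share of outcome variance due to subtype, agrees. A 20% share at a 24/21 split corresponds to d = 1.00, and power was 66.5% against 75.2% (SE ratio 1.126).

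**Step 3: main effect or subtype-by-visit.** If the gap grows over visits to 1 SD at Week 12 (8/7), VIIS power with subtype omitted / main effect / subtype-by-visit is 73.5 / 75.3 / 75.6% at Visit 4 and 71.3 / 75.5 / 75.8% at Visit 5. The main effect recovers most of the loss.

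**Step 4: log-rank** (40,000 trials per cell; 15 v 15; treatment hazard ratio 2.5; 30% of vehicle subjects responding by Week 12; events seen at Weeks 2, 4, 8 and 12). Power is unstratified v stratified.

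| Split | Subtype HR 1 | HR 2 | HR 4 |
|---|---|---|---|
| 8/7 | 36.9 v 36.6% | 34.4 v 36.3% | 27.6 v 34.9% |
| 12/3, larger subtype faster | 37.1 v 36.6% | 35.4 v 36.4% | 33.3 v 36.8% |
| 12/3, smaller subtype faster | 37.1 v 36.8% | 34.3 v 35.3% | 27.8 v 34.0% |

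**Step 5: if balance fails.** Suppose SAP 5.2 means one unblocked list of 45 per subtype (an assumption). A single-visit ANCOVA, not an MMRM, then gives omitted v added at d = 0, 0.25, 0.5 and 1:

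- 24/21 subjects: 74.5 v 73.9, 73.3 v 73.3, 71.6 v 73.5, 65.1 v 73.7%.
- 36/9 subjects: 74.7 v 73.9, 73.6 v 73.2, 73.2 v 74.1, 68.8 v 74.2%.

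Adjusting costs 0.6 to 0.8 point at d = 0. It breaks even near 0.25 SD at 24/21 and between 0.25 and 0.5 SD at 36/9. Mean estimates stayed within 0.01 of the true 1.00 either way.

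**The case against.** The strongest reply is that this is a preference and not an error. The SAP reproduces the protocol's model, the affected analyses are other-secondary or exploratory, and the study claims no power. Baseline is already a covariate, so only a subtype effect beyond Baseline counts, and the documents give no evidence of one. All of that stands, and it is why the point is an improvement and not a correction. It does not remove the case for the change: the sponsor chose subtype for stratification and for its two leading tests, and the possible gain exceeds the possible cost.

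The log-rank part is weaker, and that also stands. The gain at a subtype hazard ratio of 2 is only 1 to 2 points, and the three exploratory tests are meant to describe times, so lost power matters little there. A reader may worry that a sparse subtype would break the stratified test. It need not: a stratum with no events, or only one arm, contributes zero. In simulated 14/1 splits, 29 to 72% of trials had a stratum with no events and the statistic could always be computed.

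Three stronger readings are tempting, and the documents do not support them:

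- **The SAP departs from the protocol.** It does not. The omission is in both, so on this point Section 11 is correct in reporting no change.
- **The omission biases results or creates false positives.** With balance and complete data, the MMRM estimate is unbiased and the test conservative.
- **The main efficacy conclusion is affected.** The primary and key secondary tests are already stratified.

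**Conclusion.** The point holds as a low-severity improvement. CI subtype is missing from four MMRMs (two other-secondary, two exploratory) and from the log-rank test of time to VIIS-50. It is also missing from three descriptive log-rank tests, where it matters little.

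If subtype is prognostic beyond Baseline, the MMRM treatment estimates stay unbiased but their standard errors are overstated. That statement needs balance within subtype, and either complete data or missingness that does not depend on subtype given the modelled data. The last condition matters because SAP 5.6.1 analyses observed data without imputation.

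Under the assumed inputs, adding subtype gains about 0 to 2 points of MMRM power for gaps up to 0.5 SD and about 5 to 9 points at 1 SD. For time to VIIS-50 the gain is about 1 to 2 points at a subtype hazard ratio of 2. The omission itself is certain from the text; the size of the gain is not, because the documents give no subtype effect, split, SD or treatment effect.

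**What to change.** Before unblinding:

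1. Add CI subtype as a fixed effect to the four VIIS and I-NRS MMRMs. A main effect is enough; if subtype-by-visit is wanted, fix that choice in advance too.
2. Make the log-rank test of time to VIIS-50 stratified by CI subtype, with the unstratified test as a sensitivity analysis and no fallback that depends on the observed events. Stratifying the three exploratory log-rank tests is optional.
3. Record both changes in SAP Section 11 as departures from the protocol's model.

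The cost is SAP wording, one model term with one degree of freedom, and one stratification variable; no new data are needed. If subtype turns out not to be prognostic, the power cost is about 0.1 point for the MMRMs with balance within subtype, about 0.6 to 0.8 point if the lists are unblocked (single-visit ANCOVA figure), and 0.3 to 0.5 point for the log-rank test.
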